The following five school districts in St. Louis County will be included: University City, Ferguson-Florissant, Normandy, Pattonville, and Jennings. Individuals who are students, staff, and household members of students and staff are eligible to participate in the various parts of the study. Sixteen middle and high schools from these school districts will participate. According to St. Louis County and regional hospital data, these districts are located in areas that have been most heavily impacted by COVID-19, especially in the early months of the pandemic. Additionally, all schools in this study receive Title 1 funding and have 100% of their students receiving free and reduced lunch. The percent of in-person attendance when available ranges from 20%-42%, and 18%-42% of families in these districts live below the poverty line.

D Study Procedures

D1 Testing Study Procedures

Recruitment and Consent

All research activities will occur among the students, parents/guardians, staff (teachers, aides, nurses, administrators) and household members of our participating school districts. All students (5-21 years old), school staff, and their household members (all ages) are eligible for inclusion in the study. Individuals will be excluded if they (or their parents/LAR) do not provide consent or are unable to provide saliva for testing.

Screening Testing Consent

Prior to starting screening testing, students, staff, and their household members will be consented or assented in-person (group or individual discussion), by phone, or by zoom. Middle and high school students under the age of 18 will provide assent (if cognitively able) for participation after we have obtained consent from their parent/LAR by phone, zoom or in person. Since household members/parents/LARs are not present in the school, they may receive a copy of the consent document prior to the consent discussion.

Symptomatic/Exposure Testing Consent

For symptomatic and/or exposure testing, we will obtain verbal consent and assent (when appropriate) prior to testing. A copy of the consent information will be provided. We will also have individuals sign an email communication form and note their email preferences. The email communication form might be in person or electronic since parents/LARs are not present at the school.

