Power calculation: A cluster randomized trial (CRT) will be conducted at 12 schools that provide symptomatic SARS-CoV-2 testing to students and staff. Schools will be randomized 1:1 to either screening testing plus symptomatic testing, or symptomatic testing only. All participants including students and staff will receive the same assignment within a given school. The primary outcome is transmission rate, defined as the ratio of the number of contacts testing positive for SARS-CoV-2 to total number of contacts for each school-based case. We hypothesize that schools performing screening testing will have lower transmission rates than routine symptomatic testing. We expect that transmission rates with screening testing or routine symptomatic testing will be 2% and 8%, respectively. With the assumptions that the intracluster correlation coefficient (ICC) is 0.02 and the standard deviation of transmission rate is 0.22, 6 schools in each arm with an average of 117 participants per school will achieve 80% power to detect a difference in transmission rates between the two study arms using a two-sided t-test at a significance level of 0.05 (Table 3). PASS 15.0 was used to conduct this power analysis.

Table 3. Sample Size

| ICC | Standard deviation | # of participant per school |
|------|--------------------|-----------------------------|
| 0.01 | 0.25 | 83 |
| | 0.30 | 188 |
| | 0.33 | 376 |
| | 0.35 | 803 |
| 0.02 | 0.22 | 117 |
| | 0.23 | 164 |
| | 0.24 | 252 |
| | 0.25 | 486 |
| 0.03 | 0.20 | 221 |
| | 0.21 | 806 |

Analysis plan: The generalized estimating equation (GEE) model with appropriate link function (e.g., identity for primary outcome) will be used to analyze the CRT data, in which the correlation among participants within each school needs to be considered. The autoregressive of first order as a working correlation structure will be used, and participants with missing values will be excluded from the GEE analysis. The GEE model includes the group indicator and other potential factors, including: race/ethnicity, insurance status, age, gender, underlying diagnoses, masking, distancing, ventilation, location of transmission. Least square means for the primary outcome per group will be estimated, and the standard errors will be calculated with the GEE sandwich method when accounting for within-school correlation. All analyses will be conducted using SAS (SAS Institute, Cary, NC) at the two-sided significance level of 0.05.

Data Management.

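### The primary GEE lists nine further factors on about 12 schools; any that vary mainly between schools inflate the false-positive rate or, once the standard error is corrected, cost power

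*Combined protocol and SAP*

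**What the plan says.** Section E (Analysis plan) fits a GEE with the group indicator and other potential factors, among them "race/ethnicity, insurance status, age, gender, underlying diagnoses, masking, distancing, ventilation, location of transmission". The working correlation is first-order autoregressive and the standard errors come from the sandwich estimator. The plan gives no small-sample correction, no t reference distribution, no coding of the factors and no rule for which of them enter. The test level is fixed: "All analyses will be conducted using SAS (SAS Institute, Cary, NC) at the two-sided significance level of 0.05".

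Section E (Power calculation) describes a different analysis, an unadjusted comparison of two arms by t-test: "6 schools in each arm with an average of 117 participants per school will achieve 80% power". It assumes "transmission rates with screening testing or routine symptomatic testing will be 2% and 8%, respectively" and "intracluster correlation coefficient (ICC) is 0.02 and the standard deviation of transmission rate is 0.22". The unit of allocation is the school: "Schools will be randomized 1:1 to either screening testing plus symptomatic testing, or symptomatic testing only".

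The number of schools is not consistent. Section E says "A cluster randomized trial (CRT) will be conducted at 12 schools", and the Introduction also gives 12. Section C (Study Setting and Populations) says "Sixteen middle and high schools from these school districts will participate", and the Screening Testing paragraph of section D1 assigns eight of sixteen to screening.

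**The concern.** Arm is constant within a school, so its effect is estimated from contrasts between schools. With 12 schools and arm alone, 10 between-school degrees of freedom remain. Every further covariate that is constant within schools, or nearly so, uses one of them and by chance is partly collinear with arm. This does two things. It makes the plain sandwich more optimistic than it already is with few clusters. It also raises the true standard error of the arm effect, which no variance correction can undo.

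The documents leave open how many of the nine factors are of that kind. Ventilation is named only in the analysis plan, and the protocol text describes no person-level source for it. Masking and distancing appear in a school-level survey (section D1, Assessment of School Mitigation Strategies) and also in individual records. At stake are the type I error and the power of the primary test. The model is also open: the choice of factors, and of their level, could be made after the data are seen.

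**Working it through.** **1. Reproducing the stated power.** Inputs from section E: 6 schools per arm, 117 per school, ICC 0.02, SD 0.22, difference 0.08 - 0.02 = 0.06, two-sided 0.05.

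- Design effect: 1 + 116 × 0.02 = 3.32.
- Effective number per arm: 6 × 117 / 3.32 = 211.4.
- SE of the difference: 0.22 × √(2/211.4) = 0.0214.
- Normal reference: 0.06 / 0.0214 = 2.80, power 80.1%. The stated 80% reproduces, and all ten rows of Table 3 give 80.0-80.2% in the same way.
- t on 10 between-school degrees of freedom: power 71.5%.

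So the stated figure contains no covariates and no allowance for having only 12 clusters.

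**2. What a school-level covariate does, algebraically.** In a school-level analysis, SE² = (SD² × 3.32 / 117) / R. Here R is the residual sum of squares of the arm indicator after regression on the school-level covariates. Without covariates R = 12/4 = 3, which gives 0.0214 again. With q unrelated normal covariates and K schools, the average of 1/R is inflated by (K - 3)/(K - 3 - q). For K = 12 and q = 3 this is 9/6 = 1.5, so the SE rises by √1.5 - 1 = 22%. For K = 16 it is 13/10 = 1.3, or 14%. The inflation depends on q, not on the total number of parameters.

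Power of the corresponding t analysis on K - 2 - q degrees of freedom, averaged over chance imbalance:

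| School-level covariates | 12 schools | 16 schools |
|---|---|---|
| 0 | 71.5% | 85.3% |
| 1 | 66% | 82% |
| 2 | 60% | 78% |
| 3 | 54% | 74% |

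**3. Simulation of the planned type of model.** The assumed coding is intercept, arm and 12 covariate columns (14 parameters: three levels each for race, insurance and location, and one column for each other factor). Schools have equal size (117), the covariates are unrelated to outcome and no data are missing. The ranges pool beta-binomial and normal outcomes, with 1,500-3,000 replicates per setting; Monte Carlo error is about 1 point. Size is for the uncorrected sandwich with a normal reference. Power is for 8% against 2% with a corrected sandwich and t degrees of freedom.

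| 12 schools | Uncorrected size | Corrected power |
|---|---|---|
| Arm only | about 10% | 64-72% |
| All covariates person-level | 9-14%; up to 18% if 15-30% of their variance is between schools | 53-75% |
| One school-level factor | about 15% | 53-68% |
| Three school-level factors | 20-27% | 27-33% Mancl-DeRouen; 53-58% Kauermann-Carroll |

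With three school-level factors the simulated SE of the arm effect rose from 0.0214 to 0.0277 (+29%) in one set-up and from 0.0213 to 0.0265 (+24%) in another. This is in line with the 22% from step 2, plus a contribution from person-level columns that also differ somewhat between schools.

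**4. Sixteen schools.** Across the same settings, size is about 9-18% and corrected power about 55-87%.

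**The case against.** The strongest reply is that most of the nine factors are person-level, so the list does little harm. Much of this stands. Section D1 (Assessment of School-based Transmission) records distance, masking and place of exposure for each case-contact pair. The interview items ask individuals how much of the time they were masked and distanced. The school survey is optional. Age varies within schools because staff are included; the milestones expect 50%-60% of tests in adult staff. On this reading ventilation is the one likely school-level factor, and the relevant figures are about 15% size and 53-68% corrected power. The reply does not remove the point, because the plan does not say which source supplies masking and distancing.

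Three stronger readings are tempting, and the documents do not support them.

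- A reader might infer that 14 parameters on 12 schools is itself the fault. The plan gives no coding, so 14 is an assumption, and the same 14 parameters cost almost nothing when the covariates vary only within schools.
- A reader might infer that the test cannot be computed. The school score contributions sum to zero, so the sandwich matrix has rank at most 11. That blocks a joint test of all 14 parameters, not the one-degree-of-freedom test of arm.
- A reader might charge the whole inflated error rate to the covariates, or quote power of about 33% as the expected result. About 10% arises with arm alone. The 27-33% needs three school-level factors and the Mancl-DeRouen correction, which is conservative there (true size about 2-2.5%). Kauermann-Carroll gives 53-58% in the same setting, at a size of about 6-8%.

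Finally, the covariates were simulated as unrelated to outcome. Masking, distance and location plausibly predict transmission and could return some precision; how much cannot be worked out from the documents.

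**Conclusion.** The point holds in a limited form. The primary model is open-ended, its power statement belongs to a different and unadjusted test, and any factor that varies mainly between schools damages the arm comparison. At 12 schools the uncorrected false-positive rate runs from about 10% to 27%, depending on how many factors are school-level. After correction, three such factors leave power well below 80% under either correction. Purely person-level factors add little beyond what the uncorrected sandwich already does wrong. With sixteen schools the problem shrinks but does not vanish.

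These sizes rest on the assumed 14-parameter coding, non-prognostic covariates, equal school sizes and complete data. The number of school-level factors is unknown, so the result is a range and not a single figure. Severity: should-fix.

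**What to change.** In section E (Analysis plan):

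- Limit the primary model to arm, any randomisation strata, and at most one or two covariates that are named in the plan and measured before randomisation. Choose them without sight of outcomes by arm.
- Move the remaining factors to a model labelled exploratory. State for each its source, its coding, and whether it is recorded by person or by school.
- Specify a small-sample correction to the sandwich with t degrees of freedom based on the number of schools. Shortening the list does not replace this, because the arm-only model already has about 10% false positives.
- State that the power figure refers to the reduced model. On a t reference the plan's own inputs give 71.5% with 12 schools and 85.3% with sixteen.
- Reconcile the 12 schools of the Introduction and section E with the sixteen of sections C and D1.

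The cost is wording only. The downside is less adjustment for prognostic factors in the primary model; the fuller model is still reported as exploratory.

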Follow-up Protocols: Testing results will be available within 24 to 72 hours. All students, staff, and household members with positive results will be notified by [name] and/or a member of the study team and information regarding appropriate isolation and quarantining for contacts will be provided to comply with prevailing National/County health department recommendations. Additional financial and social services needed for the student and family due to isolation and/or quarantine procedures may be coordinated with the school and community partners. Finally, all positive individuals may have a 3-week phone call follow-up to inquire about the outcome of their illness including the need to seek medical attention and/or be hospitalized. For those in the contact arm, there might be additional questions if the

individual tests positive related to: activities, behaviors, and potential school based exposures.

Assessment of School Mitigation Strategies: Ascertaining the mitigation practices in place for each school is essential for evaluating the impact of additional testing on school transmission. A school-based mitigation strategy survey (Appendix 1), developed in conjunction with the CDC and utilized in prior school-based investigations, may be completed by each school at the beginning of the project. Questions in this survey will include: method of instruction (e.g., hybrid, type of hybrid, fully in-person) and date implemented, masking recommendations and perceived compliance, distancing in classrooms, use of physical barriers (e.g., Plexiglas), location and processes for eating lunch, and mitigation strategies used in extracurricular activities (e.g., sports, choir, band). Schools will also be asked about their quarantine rates and new school based cases/contacts on a weekly basis. This will help understand the rates of transmission in the schools.

Assessment of School-based Transmission: The primary outcome for this study will be the average of the secondary attack rate of school-based transmission per case at each school. For example, if a case has 10 contacts and 2 become infected, the secondary attack rate for that case would be 20%.

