School-based transmission will be determined by two methods. First, all close contacts of an infectious case in the school, identified through contact tracing by school staff and administrators, will be approached to participate in the study (as described above). Those electing to participate will undergo a contact interview (Appendix 2) to understand their behaviors and potential other COVID-19 exposures. Furthermore, the school contact tracer will complete a survey on the relationship of the case to each contact that provides information on the location of the exposure (e.g., classroom, lunch, extracurricular activity), distance between case and contact, use of barriers, masking adherence, and total amount of time the contact was exposed to the case (Appendix 3). The contacts will be offered testing 5-7 days after a school exposure. All contacts testing positive will undergo an independent review by five study team members using the information obtained from the case interview, contact interview, and contact tracing interview to determine whether a school-based transmission has occurred. These transmission events will be classified into the following categories with standardized definitions that were developed in conjunction with the CDC: probable, possible, unlikely, and unable to determine.

The second method to evaluate school-based transmission will be to collect weekly data from the schools, as participation in the above individual assessments is unlikely to reach 100%. The additional data to be collected will include total number of new staff and student cases, total number of new contacts, and number of school-based contacts that become new cases during their quarantine period. The secondary transmission rate will be calculated based on the number of positive school-based contacts per positive case. This method will provide the most conservative/greatest estimate of school-based transmission without knowledge of an individual's exposure to a potential household or community case.

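### The only primary model can adjust for exposure-level masking, distancing and location recorded after schools are allocated, and it drops participants with missing values

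*Combined protocol and SAP*

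**What the plan says.** Section E (Analysis plan) describes a single GEE: "The GEE model includes the group indicator and other potential factors". The named factors are race/ethnicity, insurance status, age and gender, followed by "underlying diagnoses, masking, distancing, ventilation, location of transmission". The effect estimate comes from this model: "Least square means for the primary outcome per group will be estimated". The missing-data rule is that "participants with missing values will be excluded from the GEE analysis". Section E states no unadjusted model, no rule for choosing among the factors, no imputation and no sensitivity analysis.

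Section D1 offers several possible sources for the mitigation factors:

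- **Contact tracer's survey** (Assessment of School-based Transmission). After a school case, "the school contact tracer will complete a survey on the relationship of the case to each contact". It covers the location of the exposure and "distance between case and contact, use of barriers, masking adherence".
- **Case and contact interviews and the data elements survey** (Contact/Data Elements Survey). Both ask individuals for the percentage of time they wear a mask, can keep their distance, and are within 6 feet of others.
- **School mitigation survey** (Assessment of School Mitigation Strategies). It covers masking and distancing for the whole school and "may be completed by each school at the beginning of the project". The same paragraph calls knowledge of mitigation practices "essential for evaluating the impact of additional testing on school transmission".

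Location of transmission, as a named variable, appears only in the Analysis plan.

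**The concern.** The trial asks what happens when a school is allocated to weekly screening. A covariate measured after allocation can itself respond to allocation. Weekly testing might relax masking and distancing through reassurance, or strengthen them through attention. Holding such a covariate fixed removes or inflates part of the effect that the trial is meant to measure.

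The missing-data rule adds a second route to trouble, because a covariate that is missing for reasons tied to the outcome decides who stays in the analysis.

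Neither risk can be checked against the plan, since the factors are only potential and their source forms are not named. The choice could therefore be made after the data are known. Section F has the investigators and the trial statistician reviewing data each quarter for differences between the two strategies, which is a further reason to fix the model beforehand.

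**Working it through.** **1. Timing of each possible source.**

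| Factor | Possible source | When recorded |
|---|---|---|
| Location | Contact tracer's survey (location of exposure) | After a case arises in an allocated school |
| Masking, distancing | Contact tracer's survey | After a case arises in an allocated school |
| Masking, distancing | Case or contact interview | After a case arises in an allocated school |
| Masking, distancing | Data elements survey | Asked of people who consent to screening, have symptomatic testing or are identified in contact tracing |
| Masking, distancing | School survey | Project start; optional; timing relative to randomisation not stated |

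Only the school survey could plausibly precede any effect of allocation, and it is not a clear source for location.

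**2. Effect of adjusting for a post-allocation factor.** The planned rates are 8% and 2% (Section E), a difference of 6.0 points. The other inputs are assumed: masked contacts have 3 points lower risk, 60% are masked in control schools, and 45% or 75% in screened schools.

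- Control: 0.60 × 6.8% + 0.40 × 9.8% = 8.0%.
- Screened, 45% masked: 0.45 × 0.35% + 0.55 × 3.35% = 2.0%. Difference within each masking stratum: 6.8 − 0.35 = 6.45 points.
- Screened, 75% masked: 0.75 × 1.25% + 0.25 × 4.25% = 2.0%. Difference within each stratum: 6.8 − 1.25 = 5.55 points.

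The shift is the masking effect times the difference in masking: 3 × 0.15 = 0.45 points, in either direction. A reader with other inputs can scale it.

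**3. Exclusion that depends on the outcome.** Suppose location has a value only where transmission occurred.

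- If contacts are the records, only positive contacts are complete, and the rate is 100% in both arms.
- If cases are the records, every case with no transmission drops out. In Section D1's example of a case with 10 contacts, the smallest ratio that could remain is 1/10 = 10%, above both planned rates.

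A milder version (assumed): 10% of positive and 30% of negative contacts lack a value. The true 2% appears as 0.02 × 0.9 / (0.02 × 0.9 + 0.98 × 0.7) = 2.6%. The true 8% appears as 0.08 × 0.9 / (0.08 × 0.9 + 0.92 × 0.7) = 10.1%. The difference becomes 7.5 points instead of 6.0.

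**4. Loss of power from exclusion.** Inputs from Section E: difference 0.06, SD 0.22, ICC 0.02, 6 schools per arm, m = 117 per school, two-sided 0.05.

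SE = 0.22 × √[ (1 + (m − 1) × 0.02)/m × (1/k₁ + 1/k₂) ], with power from a non-central t on m(k₁ + k₂) − 2 degrees of freedom.

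The plan's own figure comes first: with m = 117, SE = 0.22 × √(3.32/117 × 2/6) = 0.0214, and 0.06/0.0214 = 2.80. Power is 80.0%, as the plan states, with no allowance for exclusions.

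| Retained per school (assumed) | 6 schools per arm | 8 per arm (Section D1, Screening Testing) |
|---|---|---|
| 117 (all) | 80.0% | 89.9% |
| 106 (about 90%) | 78.8% | 89.0% |
| 100 (about 86%) | 78.1% | 88.5% |

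If a whole school lacked a covariate that the model uses (assumed), power at m = 117 would be 76.2% with 6 and 5 schools, and 72.5% with 5 and 5. Starting from 8 per arm, it would be 87.8% with 8 and 7, and 85.7% with 7 and 7.

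**The case against.** The strongest reply is that the factors are only potential, so nothing commits the team to fit exposure-level masking, distancing or location. Masking and distancing could be taken from the school survey, and location of transmission may simply mean the location of exposure, which is collected for contacts whether or not they become infected. All of this is possible. It shows that a defensible version of the model exists, but the plan does not select it.

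Four stronger readings are tempting, and the documents do not support them.

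- A reader might infer that the adjusted estimate will be biased. Nothing in the documents shows that allocation changes masking, distancing or location, and nothing excludes it.
- A reader might infer that whole schools will be lost. That needs the school survey to be the source, the factor to be kept in the model, and a school not to complete the form. The permissive wording may be only drafting style, given how important the same paragraph says the information is.
- A reader might infer that contact-level items cannot be fitted to a per-case ratio. A case interview can give one value per case, and Section E powers and models participants, so the unit of analysis is itself unresolved.
- A reader might infer that ventilation is not collected. The appendix forms are not shown.

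It is also fair to say that a group-only model is not a clean estimate of the effect of allocation. Screening can change which cases are detected and which contacts are traced, and the outcome is defined within those. Adjusting for exposure setting could be a deliberate attempt to balance case mix. That is a reason to report the adjusted analysis, labelled as such, but not to make it the only one.

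**Conclusion.** The point stands as a risk in how the primary analysis is specified. The only stated model can include factors recorded after allocation, their sources are not named, and missing values remove participants.

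The size of any adjustment bias cannot be derived from the documents. The illustration gives 0.45 of 6.0 points in either direction, on assumed inputs. Selection on the outcome could be severe, but only if location is recorded solely where transmission occurred, which the documents do not state. Ordinary loss of participants costs about 1 to 2 power points at 86% to 90% retention, and more only if a whole school lacks a covariate. The planned sample size is not wrong on its own inputs.

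This should be fixed before the model is fitted; confidence is medium.

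**What to change.** - Make the primary model group alone, or group plus a short fixed list of pre-allocation characteristics, for example school level (middle or high), age, and student or staff.
- Move exposure-level location, masking and distancing to a labelled secondary analysis. Name the source form of each, and define location so that it exists for infected and uninfected contacts alike.
- Do not let a missing covariate remove anyone from the primary analysis. Either fit the group-only model to everyone with an outcome, or impute baseline covariates with a method that respects clustering by school.

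The cost is a change of SAP wording and, if covariates are kept, imputation code; no new data are needed. The primary model gives up adjustment for exposure setting. The change does not remove selection through which cases are detected and which contacts are traced, and the report should say so.
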